1.2 Secondary Objectives

- a) To assess the incidence and severity of Graft Versus Host Disease (GVHD), after conventional induction therapy followed by adoptive immunotherapy with NIMA compatible, IPA targeted CBU.
- b) To assess the incidence and severity of GVHD, after conventional induction therapy followed by adoptive immunotherapy with haplo-identical stem cells.
- c) To study kinetics of graft chimerism (including UCBM-microchimerism) after each of these treatments
- d) To study development of HLA-antibodies after each of these treatments
- e) To assess response rates and duration of response after each of these treatments
- f) To assess the utilization of unrelated, low cell dose CBU as adoptive immunotherapy for AML

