7.4 Response Assessment

A bone marrow examination to document response must be performed in all patients on or before Day 60. Physicians should consider earlier bone marrow exams in patients whose peripheral blood counts are not recovering or recovering sluggishly. Subsequent treatment (consolidation, salvage therapy, etc) will be at the discretion of the treating physician.

Patients will continue to be followed for survival, and disease status. Samples for correlative studies will be collected, if possible at 2 month intervals after day 60, until one year after treatment.

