10.2 Stopping Rules

The occurrence of adverse events that are life-threatening, lead to ICU admission or death (as defined in section 8.3) will lead to temporary suspension of enrollment and immediate assessment of events.

The study will also be paused if there is death that is directly attributed to infusion of adoptive cell therapy; for example severe infusion related reaction, infection from contaminated unit, Grade 5 GVHD etc.

Enrollment may resume upon assessment by the investigators that there are no safety issues and upon appropriate revision of the protocol – if required.

After 10 patients are enrolled in each group, the incidence of the above-defined life-threatening complications will be assessed. If more than one patient out of 10 enrolled patients (i.e., $>10\%$) in a cohort experiences either of these complications, the cohort will be stopped for safety. Each cohort will be evaluated separately with respect to these complications. Additionally, if three or more of the first five patients in a particular cohort experiences either of these complications, the cohort will also be stopped. This is illustrated in the Table below.

N treated subjects	5	10	15	20
No with gr III-IV GVHD to trigger stopping rules	2	2	3	4
No with prolonged myelosuppression to trigger stopping rules	2	2	3	4
No with either Gr III-IV GVHD or with prolonged myelosuppression to trigger stopping rules	3			

For assessment of secondary objectives, descriptive statistics will be utilized via the method of binary proportions and 95% confidence intervals will be calculated to assess the precision of the obtained estimates. All analyses will be performed in SAS Version 9.3 (SAS Institute, Inc., Cary, NC) and Stata Version 13.0 (StataCorp, College Station, TX).

Addendum 5/26/2020: To date stopping rules have not been met in the CBU cohort after enrolling more than 30 patients. The Haplo cohort has not accrued.

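### Binary proportions are the only method named for the secondary objectives, but two of them, duration of response and chimerism kinetics, cannot be answered by a proportion

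*Combined protocol and SAP*

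**What the plan says.** The analysis of secondary objectives is one sentence at the end of Section 10.2: "For assessment of secondary objectives, descriptive statistics will be utilized via the method of binary proportions", with 95% confidence intervals. The next sentence names SAS and Stata. No objective is excepted and no other method is named.

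Section 1.2 lists six secondary objectives. Sorted by the kind of outcome they describe:

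- (a) and (b), GVHD with CBU and with haplo-identical cells: incidence (binary, or time to event) and severity (ordinal).
- (c) "To study kinetics of graft chimerism (including UCBM-microchimerism) after each of these treatments": a measure repeated over time.
- (d) "To study development of HLA-antibodies after each of these treatments": naturally binary.
- (e) "To assess response rates and duration of response after each of these treatments": one binary outcome and one time-to-event outcome.
- (f), use of low-cell-dose CBU: descriptive.

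Other sections that bear on the point:

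- Section 7.4 requires a marrow by day 60 and continues follow-up for survival and disease status with no stated end. It adds: "Subsequent treatment (consolidation, salvage therapy, etc) will be at the discretion of the treating physician".
- The schedule in Section 7.1 has weekly chimerism to day 60. Its later column applies only to patients who show donor chimerism, and it has no marrow entry after day 60.
- Section 9 defines response, relapse, and times to neutrophil and platelet recovery. It gives no analysis method for any of them.
- The May 2020 addendum in Section 10.1 raises the CBU cohort to 60 treated patients and says that this size will settle the efficacy question.

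**The concern.** A proportion answers how many patients had an event by some point. It does not say how long responses last or how chimerism rises and falls. The plan gives no start date, end date, censoring rule or landmark day for response duration, so even a deliberately reduced binary version is undefined.

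Duration of response is half of the plan's listed efficacy objective. If the 60-patient cohort is to carry a firm efficacy conclusion, its method should be fixed in advance. As written, the analyst must either leave objective (e) half answered or choose a method after seeing the data.

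Censoring is foreseeable. Accrual was extended in 2017 and again in 2020, so follow-up will be unequal unless the analysis waits for the last patients. Later treatment is discretionary and has no handling rule.

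**Working it through.** **The plan's own figure.** Section 10.1 states a half-width of 13.1% for a complication proportion of 10% with 20 patients per cohort: 1.96 × √(0.10 × 0.90 / 20) = 0.1315. It reproduces. At 60 patients the same formula gives 0.0759, or 7.6%. Both concern the primary safety endpoints. The plan states no precision for any secondary objective.

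**Input for the illustration.** The median CR duration of 7 months comes from the historical second-salvage series in Section 2.1. It is not a prediction for this trial. With exponential durations the hazard is λ = ln 2 / 7 = 0.0990 per month, and the 12-month relapse risk is 1 − exp(−12λ) = 1 − 0.305 = 69.5%.

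**Step 1: a proportion does not identify duration.** Take Weibull curves that all give 69.5% relapsed at 12 months, with complete follow-up. Their median is 12 × (7/12)^(1/k) for shape k.

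| Shape k | Median duration (months) |
|---|---|
| 0.5 | 4.1 |
| 1 | 7.0 |
| 2 | 9.2 |

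The same proportion therefore fits medians that differ more than twofold.

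**Step 2: incomplete follow-up.** Assume independent exponential censoring at rate c. The crude proportion of all responders seen to relapse by 12 months is λ/(λ + c) × [1 − exp(−12(λ + c))]. The last column drops responders censored before 12 months.

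| Censored by 12 months (assumed) | Crude, all responders | Censored dropped |
|---|---|---|
| 0% | 69.5% | 69.5% |
| 10% | 66.6% | 70.8% |
| 20% | 63.7% | 72.3% |
| 30% | 60.5% | 73.9% |
| 50% | 53.5% | 77.8% |

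Against 69.5%, the crude figure is 2.9 to 16.0 points low. Dropping censored patients makes it 1.3 to 8.3 points high.

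**Step 3: competing death.** Let non-relapse death be a share f of the total hazard, with the total still giving a 7-month median and follow-up complete. The crude relapse proportion is (1 − f) × 69.5%, which is exactly the cumulative incidence. One minus Kaplan-Meier with deaths censored is 1 − exp(−12λ(1 − f)).

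| f (assumed) | Crude = cumulative incidence | 1 − KM, deaths censored |
|---|---|---|
| 20% | 55.6% | 61.3% |
| 35% | 45.2% | 53.8% |
| 50% | 34.8% | 44.8% |

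Competing death alone does not bias the proportion. A Kaplan-Meier analysis of relapse that censors deaths would be the worse choice, so the fix must say how death counts.

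**Chimerism.** No arithmetic is needed. Weekly values to day 60 form a profile over time, and one proportion discards the timing that objective (c) asks about. After day 60 the schedule conditions on the outcome itself, so later values describe only patients who still carry donor cells. A different estimator would not cure that.

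**The case against.** The strongest reply is that this is a pilot with a primary safety objective, no formal comparison between cohorts and descriptive secondary aims. No stopping rule depends on the secondary outcomes, and an analyst would probably draw a Kaplan-Meier curve anyway. The first part is true and limits the severity. It does not explain why the plan names a method that cannot deliver two of its own objectives, and the addendum's efficacy claim goes beyond a pilot.

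The bias figures can also be challenged. The plan does not say that patients with short follow-up stay in a 12-month denominator, or that a relapse proportion will be reported. If analysis waited until responders had 10 to 34 months of follow-up (assumed uniform), the crude 12-month figure would be about 69.3% against 69.5%. This objection stands, so Step 2 is illustration only. Step 1 does not depend on it.

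A reader might infer more than the documents support:

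- *That every secondary objective is misfitted.* Proportions suit response rate, HLA antibodies, and GVHD incidence by a stated day with complete follow-up.
- *That time to count recovery is wrongly assigned to proportions.* It is defined in Section 9 but is not a listed secondary objective, so the sentence in Section 10.2 does not expressly cover it. It has no stated analysis method.
- *That GVHD and chimerism figures will absorb events from later grafts.* Section 7.4 does not name a later transplant. Off-protocol reinfusion in Section 5.4 concerns excess haplo-identical cells, and Section 10.2 records that the haplo cohort had not accrued by May 2020. Sections 8.2 and 10 also use attribution to the study treatment.
- *That durations would be read only from patients who relapsed, and so come out too short.* The plan describes no such practice.

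**Conclusion.** The concern holds for two items: duration of response in objective (e) and chimerism kinetics in objective (c). For both, the named method is the wrong type of summary even with perfect follow-up. A 12-month relapse proportion of 69.5% is compatible with medians of about 4 to 9 months, assuming Weibull curves with shapes 0.5 to 2 anchored on the historical 7-month median.

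Incomplete follow-up would add a bias of about 3 to 16 points under assumed censoring of 10% to 50% by 12 months, and none if follow-up is complete. The documents give no censoring rate, so these figures are not a forecast of the trial's error.

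This should be corrected but does not threaten the primary safety analysis. Section 2.6 (preliminary results) was not in the text I had, so I cannot say whether it describes an analysis of response duration.

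**What to change.** Replace the sentence in Section 10.2 with a paragraph that does the following:

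- **Binary outcomes.** Keep proportions, with exact 95% confidence intervals, for response rate, HLA antibodies and GVHD incidence by a stated day. Where follow-up to that day is incomplete, use cumulative incidence for GVHD.
- **Duration of response.** Use Kaplan-Meier from first documented CR, CRp or PR to relapse or death, censored at the last disease assessment. Alternatively, report cumulative incidence of relapse with non-relapse death as a competing event. State how later consolidation or salvage therapy is handled. If PR counts as a response, first reconcile Section 9: its marrow threshold for relapse (above 5% blasts) overlaps the range allowed in PR (5% to 24%).
- **Chimerism.** Summarise by visit. State that under the Section 7.1 schedule sampling after day 60 is limited to patients with donor chimerism, so later summaries are conditional on it.
- **Count recovery.** Report neutrophil and platelet recovery by cumulative incidence with death as a competing event.

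The cost is one paragraph and slight extra analysis work in software already named. One limitation remains: relapse dates after day 60 depend on disease-status follow-up without a fixed marrow schedule, so they will be approximate, and the report should say so.

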10.3 Screening vs Treating

We anticipate that several patients will be consented and then screened for each patient treated. The sample sizes are based on number of patients treated – not on number of patients consented.

11. CRITERIA FOR REMOVAL OF PATIENTS FROM PROTOCOL THERAPY

11.1 Duration of Treatment

Patients will continue with the therapy specified in this protocol until one of the following occurs:

- Achievement of protocol endpoint CR or CRp after induction and cellular therapy
- Failure to achieve CR or CRp
- Extraordinary Medical Circumstances: If, at any time the constraints of this protocol are detrimental to the patient's health and/or the patient no longer wishes to continue protocol therapy, remove the patient from protocol treatment. In this event.

After removal from protocol therapy, patients will continue to be followed for survival and disease status. Samples for correlative studies will continue to be collected every two months until one year after cell infusion.

12. DATA, SAMPLE AND PROTOCOL MANAGEMENT

- **Protocol Compliance:** Patients will be reviewed weekly during admission by the Study Investigators who will score the patient for standard endpoints.
- **Data Entry:** REDCap (Research Electronic Data Capture) is a free data management software system that is fully supported by the Weill-Cornell Medical Center CTSC. It is a tool for the creation of customized, secure data management systems that include Web-based data-entry forms, reporting tools, and a full array of security features including user and group based privileges, authentication using institution LDAP system, with a full audit trail of data manipulation and export procedures. REDCap is maintained on CTSC-owned servers that are backed up nightly and support encrypted (SSL-based) connections. Nationally, the software is developed, enhanced and supported through a multi-institutional consortium led by the Vanderbilt University CTSA.
- **Accuracy of Data Collection:** The Study Chairman will be the final arbiter of toxicity should a difference of opinion exist

- **Management of Research samples:** Research samples will be cryopreserved after ficolling and isolation of viable cells. The serum will be stored separately. Part of the product may be stored after DNA extraction. The samples will be stored securely. They will be coded with the key to identification of the samples kept in a secure location and available only to the PI or his delegate. Samples and appropriate clinical information may be shared with other investigators at WCMC and elsewhere, but will be de-identified. Samples will be kept indefinitely.

13.0 DATA SAFETY MONITORING BOARD

The Weill Cornell Medical College Data Safety Monitoring Board (DSMB) is being requested to review safety data and to make recommendations regarding continuation, termination, or modification to the study.

The research team will report all adverse events to the DSMB after accrual of successive sets of five patient to each arm of the protocol. The report to the DSMB will include a description of adverse events attributed to cell infusion and of patient's outcome.

14.0 REGULATORY CONSIDERATIONS

14.1 Institutional Review Board/Ethics Committee Approval

The protocol for this study has been designed in accordance with the general ethical principles outlined in the Declaration of Helsinki. The review of this protocol by the IRB/EC and the performance of all aspects of the study, including the methods used for obtaining informed consent, must also be in accordance with principles enunciated in the declaration, as well as ICH Guidelines, Title 21 of the Code of Federal Regulations (CFR), Part 50 Protection of Human Subjects and Part 56 Institutional Review Boards.

The Investigator will be responsible for preparing documents for submission to the relevant IRB/EC and obtaining written approval for this study. The approval will be obtained prior to the initiation of the study.

The approval for both the protocol and informed consent must specify the date of approval, protocol number and version, or amendment number.

Any amendments to the protocol after receipt of IRB/EC approval must be submitted for approval by the Investigator to the IRB/EC. The Investigator is also responsible for notifying the IRB/EC of any serious deviations from the protocol, or anything else that may involve added risk to subjects.

Any advertisements used to recruit subjects for the study must be reviewed and approved by the IRB/EC prior to use.

14.2 Informed Consent Procedures

The Investigator must obtain informed consent of a subject or his/her designee prior to any study related procedure as per GCP's as set forth in the CFR and ICH guidelines.

Documentation that informed consent occurred prior to the subject's entry into the study and the informed consent process should be recorded in the subject's source documents. The original consent form, signed and dated by the subject and by the person consenting the subject prior to the subject's entry into the study, must be maintained in the Investigator's study files. At the pre-admission consultation, patients will be fully informed as to the purposes and potential risks and benefits involved in this study. Patients will have ample opportunity to ask questions before consenting. Legal guardians will sign informed consent for legally incompetent patients in accordance with hospital policy.

14.3 Protecting Privacy and Confidentiality

Confidentiality will be maintained within the limits of the law. Patient names or any other identifying information will not be used in reports or publications resulting from this study. Only qualified staff from New York Presbyterian Hospital, Weill Medical College of Cornell University, the Food and Drug Administration, or other study support such as the National Cancer Institute will be able to review patient medical records.

Should direct access to medical records require a waiver or authorization separate from the subject's statement of informed consent, it is the responsibility of the Investigator to obtain such permission in writing from the appropriate individual.

14.4 Study Records Requirements

The Investigator must ensure that the records and documents pertaining to the conduct of the study and the distribution of the study drug, that is copies of CRFs and source documents (original documents, data, and records [e.g., hospital records; clinical and office charts; laboratory notes; memoranda; subject's diaries or evaluation checklists; pharmacy dispensing records; recorded data from automated instruments; copies or transcriptions certified after verification as being accurate copies; microfiches; photographic negatives, microfilm, or magnetic media; x-rays; subject files; and records kept at the pharmacy, at the laboratories, and at medico-technical departments involved in the clinical study; documents regarding subject treatment and study drug accountability; original signed informed consents, etc.]) be retained by the Investigator for as long as needed to comply with national and international regulations (generally 2 years after discontinuing clinical development or after the last marketing approval). The Investigator agrees to adhere to the document/records retention procedures by signing the protocol.

